4.1 Objectives

The specific objectives include:

- 1. To develop a training programme for volunteers to support the delivery of an online multimodal intervention.
- 2. To assess the feasibility of recruiting, training and retaining volunteers to deliver the intervention.
- 3. To assess the feasibility of recruiting and retaining older adults with frailty to the trial.

4. To determine the acceptability of the intervention and explore barriers and facilitators to the intervention to support future wider implementation.

4.2 Outcome

Exploration of the feasibility and acceptability of the intervention will help to determine whether the multi-modal volunteer-led online intervention is appropriate for further evaluation in future research, to determine sample sizes for a controlled trial and to assess whether the ideas and findings can be shaped to be relevant and sustainable. The study will also help to determine suitability of the intervention for a larger roll out of the programme across Wessex.

Through collaborations between University of Southampton, University Hospital Southampton, and Wessex AHSN, the anticipated impacts include:

- Development of training material for wider use and future implementation studies.
- Collaboration with Wessex AHSN and the National Association of Voluntary Services Manager to develop an implementation plan with the aim to roll out the intervention across the Hampshire and Isle of Wight region and nationally at a later stage.
- Dissemination of our research findings through scientific and lay platforms to encourage implementation in other settings.
- Increased participation in PA and improved nutrition support for frail older people postdischarge with potential benefit in health outcomes.

5 STUDY DESIGN and METHODS of DATA COLLECTION AND DATA ANALYIS

Study Design

A quasi-experimental mixed methods approach will be used to determine the feasibility and acceptability of implementing a volunteer-led multi-modal intervention for discharged older adults with frailty. This feasibility study will be conducted at the University Hospital Southampton NHS Foundation Trust (UHS), training hospital volunteers to deliver virtual group support for older adults discharged from UHS.

Feasibility studies are used to determine whether an intervention is appropriate for further evaluation, to determine sample sizes for controlled trials and to assess whether the ideas and findings can be shaped to be relevant and sustainable. In this study, the feasibility of training volunteers to deliver a virtual multi-modal intervention to improve older adult's functional outcome post-discharge will be assessed. The acceptability of the intervention will also be examined through qualitative interviews to explore the views and experiences of volunteers, trainers, carers and older adults involved in this study. The impact of the intervention on physical activity levels and functional outcomes will be measured. However, as this is a feasibility study, it is not powered to show any statistical difference in the outcome measure.

Intervention

The intervention duration will be 3 months. Participants will receive three group sessions per week for 1 month (weeks 1-4), twice per week for the second month (weeks 5-8), and once weekly for the last month (weeks 9-12), with a maximum of 24 sessions. The tapered nature of the intervention was chosen to provide suitable support for older adults post-discharge with the aim to gradually encourage increased self-management to foster independence post-intervention. Components of the intervention, including exercise, nutrition support and behaviour change support, will be delivered from an online platform (Zoom). Each group session will last 40-60 minutes, including 20-30 minutes of exercise

followed by 20-30 minutes of nutrition support. The components of the intervention and the training package have been adapted from the SafeFit trial [35] and will be delivered in line with behaviour change principles and emotional support to maximise participant uptake, adherence and lifestyle self-management.

Exercise: The exercise will consist of volunteer-led group progressive resistance exercise training for 20-30 minutes. To align with home-based safety considerations, the exercises will be performed seated. Seated exercise will focus on strengthening upper and lower limbs (8 major muscle groups) and enhancing whole body range of motion and flexibility, tailored specifically to meet the needs of older adults and to minimise the risks of injury. Participants will be encouraged by the volunteers to progress repetitions (aiming for 3 sets of 8 repetitions) and to gently improve range of motion. Elastic resistance bands will be introduced from Week 5 to older adults who are comfortable and ready to progress to using resistance in the exercises. Participants will be encouraged by the volunteers to increase the resistance grade if they are able to carry out the repetitions easily. Intensity will be monitored with the Resistance Intensity Scale for Exercise (RISE) [49] and the Talk Test [50], aiming for a low-moderate difficulty on RISE and 4-6 on the Talk Test. Participants will be encouraged to complete the exercises 2-3 times per week consistent with Chief Medical Office guidelines on PA and strength improvement for older adults [16]. The exercise programme has been developed and piloted from a previous ARC Wessex study that aimed to improve PA and health in community-dwelling older adults through trained volunteers [51]. Participants will be given an exercise booklet and access to an exercise video to help support engagement with the exercises and encourage un-supervised participation at home.

Nutrition support: Volunteers will work with participants to review their diet and eating habits using the Nutrition Wheel to ensure their nutrition is appropriate and they are not at risk of undernutrition [31]. The Nutrition Wheel is an interactive tool developed from the Patients Association Nutrition Checklist (PANC) and used to engage individuals in conversation about unintentional weight loss and malnutrition. The Nutrition Wheel was developed by [name] in collaboration with the Wessex AHSN and key stakeholders and charities and identifies whether an older adult may be at risk of undernutrition, providing guidance accordingly. Specifically, the Nutrition Wheel consists of 4 main questions from PANC, including 1) Are you or your family concerned that you may be underweight, or need nutritional advise? 2) Have you lost a lot of weight unintentionally in the past 3-6 months? 3) Have you noticed that your clothes or rings have become loose recently? 4) Have you recently lost your appetite and/or your interest in eating? Based on the participant's answers, they will be directed to further questions and guided to appropriate nutritional advise. Individuals identified as undernourished will be signposted to appropriate information sheets, national helplines, or if necessary, signposted to their GP/practice nurse for further advise and screening.

Behaviour change support: Volunteers will receive training in healthy conversation skills (HCS) guided by principles of Making Every Contact Count (MECC) [52, 53]. The MECC approach supports positive behaviour change through encouraging client-centred brief conversations surrounding health and well-being and will help support the delivery of the exercise and nutrition components in the current intervention. Training will enable volunteers to have the confidence and competence to deliver healthy lifestyle messages, to help encourage participants to change their behaviour through solution-focused and empowering approaches [54]. The MECC approach is underpinned by behaviour change principles from the COM-B model, highlighting both automatic and reflective processes involved in decision making and action. Through using HCS in the current intervention volunteers can help to improve participants capability and motivation to be physically active and to eat well, empowering

participants to take control of their health behaviours by building self-efficacy and a sense of control [55].

Participants will be given the option to choose between the online intervention and telephone consultations. Participants who opt for telephone consultations will be encouraged by volunteers to perform the exercises provided in the booklet and will be given nutritional advice based on the nutrition wheel. The frequency of telephone consultations will be similar to the online intervention.

Training of volunteers

Volunteers will receive a bespoke training package adapted from the SafeFit training guidance [35]. Depending upon current Government recommendations in response to the COVID-19 pandemic the training will either be delivered online by the research team, or in-person at UHS. Once the 3 training components (i.e., exercise, nutrition, and behaviour change) have been completed, volunteers will support and shadow the trainers to deliver the intervention during the first month, aiming for 2 sessions per week to be delivered by the trainers and 1 to be delivered by the volunteers with support from the trainer. After 4 weeks, volunteers will be expected to lead the sessions independently to continue supporting participants in the adherence of the intervention with continued weekly input by the trainers.

Exercise: The exercise training programme will be developed based on clinical expertise from therapists and current evidence including experience from a recently completed study [44] and an ongoing feasibility study [51]. Training will include 2 group sessions each lasting approximately 2 hours. The first training session will include a brief section teaching the theory underpinning the benefits of exercise for older adults, and will include exercise training principles, such as FITT recommendations (frequency; intensity; time; type). The remainder of the first training session will give an overview of the seated exercise content, detail exercise delivery advice (e.g., how to demonstrate and give effective teaching points), and explore exercise safety considerations (e.g., safe set-up before and during exercise, and what to do in an emergency). Volunteers will be given an exercise training manual and links to a video to practice the exercises in their own time. Time for practice (1-2 weeks) will be given before volunteers return for their second group exercise training session. The second session will focus on delivery of the seated exercises allowing volunteers to practice delivering the exercise to their peers and to obtain feedback from the group and trainer. Safety considerations will be revisited at the end of the second session. Volunteers will also receive training on how to document adverse events that occur during the exercise classes.

Following completion of group exercise training, volunteers will be offered one-to-one training and practice sessions to help support their competence and confidence in delivering the seated exercises safely and effectively. Based upon the ImPACt study it is predicted that volunteers might need 1-3 one-to-one exercise training and practice sessions with the trainer. The trainer, [name], is a research fellow and clinical exercise instructor with extensive experience delivering exercise to a range of population groups, including older adults, and within various rehabilitation settings.

Nutrition support: Volunteers will be trained to use the Nutrition Wheel by [name], supported by [name], during a 2-hour session with accompanying support materials. The training will cover principles of healthy eating, information on undernutrition (e.g., prevalence, risk

factors, identification and treatment), details on the Nutrition Wheel, and an opportunity to use the Nutrition Wheel in a role play context.

Behaviour change support: The training, which is based on Healthy Conversation Skills (HCS), will be delivered by a health psychologist ([name]). HCS training develops four key competencies: 1) asking open discovery questions ('how' and 'what' questions), 2) listening instead of making suggestions or giving advice, 3) reflecting on practice, and 4) setting goals using SMARTER (specific, measurable, action-oriented, realistic, timed, evaluated, reviewed) planning [56]. The training will be 3 hours of in-person interactive learning to support volunteers to deliver exercise and nutrition components in an encouraging, person-centred way, translating MECC principles into practice.

Digital training

To address equality of access, participants can be provided with a tablet with the online teleconferencing platform preloaded. The tablet will contain a SIM card which will enable internet access at home, particularly for participants who do not have internet access. The research fellow will act as a digital champion who will support individuals with low confidence to access the teleconferencing platform. Upon recruitment, participants will be taught how to use the tablet and to access the teleconferencing platform during their hospital stay. They will be given a digital support booklet and will be given guidance about how to stay safe online. Digital support will be available to participants throughout the trial.

Volunteer Support and Fidelity Checks

Throughout the study a peer-supported community will be established through regular online monthly volunteer meetings to discuss experiences and gain feedback from peers and trainers. The research team will work closely to support volunteers, including listening and providing any emotional support on a group and individual basis. Volunteer feedback will be integral to shaping the support that volunteers will need in delivering the intervention and ensuring volunteer well-being. In addition, trainers will conduct regular fidelity checks (once per month) to assess the quality of group sessions delivered by volunteers. The volunteers will be observed and assessed against a competency and implementation checklist, including competency checks for the exercise, nutrition, and behaviour change components. Based upon fidelity checks and volunteer feedback, extra one-to-one training sessions, emotional and confidence support, will be available if necessary.

Volunteers will be given a training manual to help support their learning and to be used as a resource during delivery of the intervention. Volunteers will also be asked to keep an attendance record during the intervention using session completion logs and will be trained to report any adverse events.

Safety during sessions

Volunteers will be encouraged to complete a pre-session screening checklist to ensure participants are safe to exercise (e.g., safe set-up of a home exercise space; feeling well; no new or worsening symptoms). Volunteers will be taught to encourage participants to exercise at their own pace, to rest when they need to, and to move within a pain-free range of motion, ensuring that participants are working at a tailored intensity. Where possible participants will be encouraged to undertake the sessions with friends or family members present and they will be asked to keep cameras on during the

sessions. If a participant feels unwell a Zoom breakout room will enable the participant's well-being to be reviewed in private by a second volunteer.

If an emergency occurs, such as an acute medical event during the session, the volunteer will encourage participants to call their GP, or 111. If concerned about collapse, the volunteer will call 999. Volunteers will have a list of participant's addresses and GPs to hand - in case of collapse. An 'escalation plan' giving clear steps to follow, depending on the emergency situation, will be given to volunteers.

Data Collection

Participant characteristics including age, gender, domicile status, weight, body mass index, malnutrition status (MUST), baseline nutritional status (e.g., use of nutritional supplements and dietician support), co-morbidities (Charlson Co-morbidity Index) [57], cognition (Mini-mental state examination; MMSE) [58] and number of medications will be recorded. Volunteer characteristics recorded will include age, occupation, qualifications, volunteering experience, and employment status.

The primary outcome measures are feasibility and acceptability of the intervention.

Feasibility

The feasibility of implementing a volunteer-led online multi-modal intervention will be assessed by determining the number of volunteers recruited, trained and retained at the end of the study, the number of intervention sessions delivered and fidelity of volunteer delivery. Moreover, participant recruitment, retention and adherence to the intervention will be measured, as well as any adverse events

Acceptability of the intervention

Interviews will be conducted among older adults (N= 6), volunteers (N= 6), and those involved in recruiting participants and training volunteers (N= 3), to determine the acceptability of the intervention and to explore barriers and enablers to the implementation of the intervention. Interviews will be semi-structured to help guide conversation whilst allowing participants the flexibility to elaborate and reflect on any meaningful experiences.

Older adults will be selected by purposive sampling to share their thoughts and views regarding the implementation of the volunteer-led sessions. To ensure a wide range of views are included in the interviews, participants will be selected to ensure equal distribution of male and female patients, ethnicities, and a representative age range. Interviews will also be conducted for volunteers leading the intervention. Discussions among volunteers are likely to generate a wider perspective of the implementation process and may provide insight into the group narrative on their experiences in delivering the intervention and their interaction with the research participants. Interviews will be conducted via telephone and will be audio-recorded for data collection purposes.

The interviews will be semi-structured and consist of several key open-ended questions that will help define the areas explored but allow the interviewer or interviewee to expand and diverge with the aim

of pursuing or developing an idea with more depth. The interview schedules will be underpinned by Normalisation Process Theory (NPT) (see below). The interviews will seek to explore the views of older adults, volunteers and trainers on the multi-component sessions, the barriers and facilitators to the intervention and suggestions for future implementation studies.

The NPT provides a set of sociological tools to understand and explain the social processes through which new or modified practice of thinking, enacting, and organizing work are operationalized in healthcare and other institutional settings. The use of an implementation theory is useful as it helps researchers identify, describe and explain important elements of the implementation process. The three core problems which the theory is concerned with are: implementation (bringing of a practice or practices into action), embedding (routine incorporation of practice or practices into everyday work of individuals and groups) and integration (reproduction and sustainability of a practice or practices among the social matrices of an organization or institution). NPT was used in the development of the study protocol as well as the online physical activity and nutrition intervention. The online NPT toolkit was used to assist in critically thinking through the processes and challenges which may arise in implementing and integrating an intervention in a complex health care setting. NPT was chosen as the framework that underpinned this study as it was systematic in its approach, easy to understand and provided a proven framework to evaluate the implementation process of this study. Determining the acceptability of the intervention through qualitative measures will aid future implementation studies.

Secondary outcome measures: The secondary outcomes will include the measurement of physical activity levels, physical function, appetite, well-being, anxiety and depression, and self-efficacy for managing chronic disease. These measures are detailed below and will be measured at baseline (in hospital), 3 months (via telephone) and 6 months (via telephone).

Physical activity: PA will be measured using the physical activity scale for the elderly (PASE) [59]. The PASE measures a broad spectrum of activities including leisure-time, household, and occupational PA during the previous 7 days, and has good stability and convergent validity within community-dwelling older adults [60].

In addition to the PASE, PA and sleep will be assessed objectively using wrist-worn accelerometers (GENEActiv, Activinsights, Kimbolton, Cambridge, UK). These devices have previously been validated for use in healthy adult populations [61] and are extensively used in clinical studies. The GENEActiv accelerometers will measure triaxial movement acceleration in gravity (g) units (1 g = 9.81 m/s²) at a frequency of 100Hz continuously over a period of 7 days. Previously validated acceleration threshold values (in older adults) will be used to quantify the time (minutes/day) spent on average in each intensity category: total PA, and separately for light, moderate, vigorous intensities and the composite category moderate-vigorous PA (MVPA) [62]. GENEActiv watches will be posted to participants to collect 7 days of objective PA levels upon discharge from hospital (baseline) and at 3 and 6 months. GENEActiv watches will be returned through pre-paid return postage.

Physical function: Barthel Index will be used to measure older adult's functional ability [63]. The Barthel Index consists of ten items and is predominantly used with patient populations and infrequently used for community-dwelling people with reasonable reliability and good responsiveness [64]. The Barthel Index scores 10 items describing ADL and mobility, with a higher number being a reflection of greater ability to function independently following hospital discharge.

Appetite: Appetite will be measured using the Simplified Nutritional Appetite Questionnaire (SNAQ) [65], which has been validated to predict weight loss in community dwelling older adults and used to predict poor health outcomes in hospitalised older people [65-67]. SNAQ is a four-item tool comprising items 1, 2, 4 and 6 of the CNAQ, assessing appetite, satiety, taste of food and number of meals per day respectively. SNAQ has a maximum score of 20, with a score of ≤14 indicating poor appetite.

Well-being: Well-being will be assessed using the Warwick-Edinburgh Well-Being Scale (WEMWBS), which comprises 14 positively worded items relating to different aspects of positive mental health, including positive affect, satisfying interpersonal relationships and positive functioning [68]. Each item is scored on a 5-point Likert scale from 1 (none of the time) to 5 (all of the time), with a higher score indicating a higher level of mental well-being. The WEMWBS is a psychometrically robust scale showing good content validity and popularity in the measurement of well-being in relation to public health [68, 69].

Depression and anxiety: The Hospital Anxiety and Depression Scale (HADS) will be used to assess anxiety and depression [70]. The questionnaire comprises seven questions for anxiety and seven questions for depression, and has been validated across multiple settings and populations [71]. A score of 0-7 is normal, 8-10 borderline abnormal, and 11-21 abnormal.

Quality of life: Quality of life will be measured using the EuroQol (EQ-5D-5L) assessment comprising a short descriptive questionnaire and a visual analogue scale (VAS) [72]. The questionnaire includes 5 domains (e.g., mobility; self-care; usual activities; pain/discomfort; and anxiety/depression) measured with 5 response levels from 'no problems' to 'extreme problems/unable'. The VAS subjectively rates health from 0 (the worst health you can imagine) to 100 (the best health you can imagine). The EQ-5D-5L has been widely used in clinical trials and population studies as a popular measure of health status [73].

Self-efficacy for managing chronic disease: A 6-item scale will be used to assess participant's self-efficacy in managing their chronic disease [74]. The scale contains items developed from the chronic disease self-management study covering domains, such as symptom control, role function, emotional functioning and communicating with health professionals [74]. Each item is scored on a 10-point Likert scale from 1 (not at all confident) to 10 (totally confident). Higher scores indicate higher self-efficacy.

Data Analysis

Quantitative data analysis

Data collected will be double entered into a secured database for analysis. Statistical analysis will be conducted using the statistical software SPSS. Descriptive statistics -median (IQR); mean (SD); number (%) – will be used to analyse the numbers of volunteers recruited, trained and retained, as well as the type and extent of progression of the resistance exercise, and duration of their activity, and patients' adherence to the intervention. Analysis of the above outcome measures will be used to develop an assessment of the feasibility of delivering this intervention. To determine suitability for a future, fully-powered effectiveness study of the intervention, outcome measures recorded at baseline will be compared to measurement at 3 and 6 months to determine if the intervention had an impact on physical activity levels measured by PASE and GENEActiv, functional outcomes including Katz, Barthel, SNAQ, HADS, WENWBS, self-efficacy and EQ-5D-5L. The distribution of each outcome measure will be assessed for normality and described using parametric or non-parametric statistics

accordingly. A basic cost-analysis of the training programme will be carried out, costing the time of clinical staff involved in delivering the training.

Qualitative data analysis

Data collected from the interviews will be transcribed verbatim and analysed using thematic analysis (TA). The audio-recordings will be transcribed by an administrative colleague within the research department who is experienced in transcribing qualitative data. TA is a method for identifying, analysing and reporting patterns or themes within data and is widely used in qualitative research [75]. There are six phases in the process of conducting TA: Phase 1 – familiarising with the data, Phase 2 – generating initial codes, Phase 3 – searching for themes, Phase 4 – reviewing themes, Phase 5 – defining and naming themes, and Phase 6 – producing the report. Analysis of qualitative data will be conducted using either Microsoft Word, or with the help of NVIVO, depending on the amount of data collected. Transcribed text will be read and coded separately and then together by two researchers. The codes will be analysed to generate concepts and ideas to determine the acceptability of the intervention, and to identify facilitators and barriers to the implementation process. The codes act as tags or labels to help catalogue key concepts embedded within the raw data. From the codes, themes will be developed to reflect the views and experiences of the community-dwelling older adults and volunteers regarding the community-based PA intervention.

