- If an emergency occurs, such as an acute medical event during the session, the volunteer will encourage participants to call their GP, or 111. If concerned about collapse, the volunteer will call 999.
- Volunteers will have a list of participant's addresses and GPs to hand in case of collapse. An
 'escalation plan' giving clear steps to follow, depending on the emergency situation, will be
 given to volunteers.
- Volunteers will be trained to support participants using the nutrition wheel and will not be
 expected to give participants specialised nutrition advice. Volunteers will be trained to
 effectively and safely signpost participants to suitable resources and health professional
 support based upon answers given from the nutrition wheel.

A potential burden for some patients could be issues with learning new technology or having minor difficulties in accessing Zoom from home. To address equality of access, participants will be provided with a tablet with the online teleconferencing platform preloaded. The tablet will contain a SIM card which will enable internet access at home, particularly for participants who do not have internet

access. The research fellow will act as a digital champion who will support individuals with low confidence to access the teleconferencing platform. Upon recruitment, participants will be taught how to use the tablet and to access the teleconferencing platform during their hospital stay. Digital support will be available to participants throughout the trial.

Participants will be given the option to choose between the online intervention and telephone consultations. Participants who opt for telephone consultations will be encouraged by volunteers to perform the exercises provided in the booklet and will be given nutritional advice. The frequency of telephone consultations will be similar to the online intervention.

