Based on your screening results you may need to escalate to the trial team for further advice before proceeding with your session – if this is the case please record this in your session completion log.

There may also be circumstances where you need to escalate during or after your session as outlined in Figure 1.

Patient safety is our highest priority, so if you have any concerns or doubts, please just call us.

KEY REMINDER: Please remember to alert the trial team to **any changes** in the participants' status such as:

- New medical diagnosis or co-morbidity
- Start of new medication and removal of a medication
- Admission to hospital or visit to A&E or GP
- New investigations that have been arranged
- New onset of symptoms or worsening of previous symptoms
- Change in known co-morbidities

Figure 1. Safety Escalation Process

Low Risk

- Defined as a scenario where telephone advice is required
- Ring Frail2Fit team on (insert number here)

Intermediate Risk

- Defined as a scenario where the volunteer is unsure whether proceeding with the session is safe or requires further advice opost session. These scenarios may or may not require further action.
- Ring Frail2Fit team on (insert number here)

Emergency Scenario

- This is defined as anything the volunteer feels is an emergency
- Ring 999 or refer participant to 999 / 111 if able
- When appropriate please alert the Frail2Fit team on (insert number here)

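### Sections 5 and 8.1 name the GP as a route in an in-session emergency; the emergency tier of the escalation plan's Figure 1 names only 999 and 111

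*Combined protocol and SAP*

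**What the plan says.** Section 5, under Safety during sessions, gives a two-part rule. The first part is "If an emergency occurs, such as an acute medical event during the session, the volunteer will encourage participants to call their GP, or 111". The second is "If concerned about collapse, the volunteer will call 999". Section 8.1 lists the same rule among its risk mitigations: "the volunteer will encourage participants to call their GP, or 111. If concerned about collapse, the volunteer will call 999". Both sections go on to say that volunteers will receive an escalation plan, which section 5 describes as "giving clear steps to follow, depending on the emergency situation, will be given to volunteers".

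That plan is the Screening and Escalation Plan at the end of the document, which Appendix 1 lists as required documentation. It says of events after the opening screen: "There may also be circumstances where you need to escalate during or after your session as outlined in Figure 1". Figure 1 has three tiers. For low and intermediate risk the instruction is "Ring Frail2Fit team on (insert number here"). For an emergency the definition is "This is defined as anything the volunteer feels is an emergency" and the action is "Ring 999 or refer participant to 999 / 111 if able", with the study team alerted when appropriate.

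**The concern.** The protocol body and the plan it points to answer the same question differently: whom to contact when a participant becomes acutely unwell in a session. The body offers the GP; the plan's emergency tier does not.

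The setting makes the wording matter. Participants are aged 65 or over, have a Clinical Frailty Scale score of 5 or more, have recently left acute medical wards, and exercise at home, with a relative or friend present only where possible. Those who respond are trained lay volunteers, eligible from age 16, who are expected to lead sessions independently after the first 4 weeks. Taken literally, the body text lets an acute event go to a GP, and through a call that the participant has to make. That could delay emergency help. The rule also stands in the risk-management section, so it is the mitigation that the protocol itself declares.

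**Working it through.** No calculation applies: the point depends on no rate, effect size, variance or sample size. The check is a side-by-side reading of the texts for one trigger, an emergency during a session.

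| Item | Sections 5 and 8.1 | Figure 1, emergency tier |
|---|---|---|
| What counts as an emergency | One example given, an acute medical event | Whatever the volunteer judges to be one |
| GP named as a route | Yes, by the participant's own call | No |
| 111 named as a route | Yes, by the participant's own call | Yes, by referring the participant |
| 999 named as a route | Yes; the volunteer calls if collapse is feared | Yes; the volunteer rings or refers the participant |
| Study team named | No | Yes, when appropriate |

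**Routes to medical help.** The body names GP, 111 and 999, which is 3. Figure 1 names 999 and 111, which is 2. Two are shared, so 3 − 2 = 1 route stands only in the body: the GP. Sections 5 and 8.1 carry the same sentences, so this is one rule stated twice and one conflict, not two.

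**Is the GP an emergency route elsewhere in the plan?** No. The plan mentions the GP in the screening question on recent contacts and in the list of status changes to report to the team. Neither is an instruction for an emergency.

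**Does the collapse sentence also conflict?** No. "If concerned about collapse, the volunteer will call 999" gives a sufficient condition for a 999 call. It contains no word that confines 999 to collapse. Figure 1 covers feared collapse within its wider definition, so a volunteer can obey both. The body is narrower here but not contradictory.

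**Which text prevails?** Three places point to Figure 1: the description of the plan in section 5, the direction on the plan's screening page to consult Figure 1 when a concern comes up, and "There may also be circumstances where you need to escalate during or after your session as outlined in Figure 1". Together they make it the likely working instruction. None says that it replaces the GP/111 sentence, which stands just before the mention of the plan in both sections. The volunteers' training manual is not among the supplied documents, so it could not be checked.

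**The case against.** The strongest reply is that the body text is a loose summary followed by a pointer to the detailed instruction. Volunteers hold the plan and are directed to Figure 1, and the plan tells them to ring the team if in doubt. Emergencies are taught in the first exercise training session and safety is revisited in the second. Trainers supervise closely in the first month, and two volunteers cover each group. On this view the difference is editorial.

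Much of that stands. It is why no misrouting can be claimed and why the point is modest. It does not remove the conflict: a pointer placed after a rule adds to the rule unless it says otherwise, and a protocol should not state a safety rule that is weaker than the plan it hands out.

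Three stronger readings are tempting, and the documents do not support them.

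- A reader might infer that sections 5 and 8.1 allow a 999 call only for collapse. They do not say so, as shown above.
- A reader might infer that chest, arm or jaw pain in mid-session has no 999 instruction, because Table 1 names it under start-of-session screening and Figure 1 does not repeat it. But Table 1 files it under the same emergency label that Figure 1 uses, with nearly the same catch-all definition. A volunteer has no textual reason to treat it differently later in the session. Naming it in Figure 1 would help, but its absence is a side point.
- A reader might infer that volunteers will in fact send emergencies to a GP. Nothing in the documents shows this.

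**Conclusion.** The concern holds as a single wording conflict: one route, the GP, named for an in-session emergency in two sections of the protocol and absent from the emergency tier of the plan that those sections point to. It should be corrected because it is safety text for frail people exercising at home and the correction is simple.

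The conclusion rests on the supplied text. Some pages were removed before review, so the absence of a precedence statement is claimed only for what could be read. The documents give no rate of in-session emergencies, so no number of affected participants is offered. No statistical figure in the plan changes.

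**What to change.** Make these changes before volunteers are trained.

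1. In sections 5 and 8.1, replace the GP/111 sentence with: *If an emergency occurs, the volunteer rings 999, or refers the participant to 999/111, following Figure 1 of the Screening and Escalation Plan, which takes precedence.*
2. Keep "If concerned about collapse, the volunteer will call 999" in both sections. It is the only supplied text that expressly requires a 999 call for feared collapse, and deleting it would leave collapse named nowhere as a trigger.
3. Keep the GP for non-emergency matters only, such as the nutrition signposting already described in section 5.
4. Optionally, list collapse and chest, arm or jaw pain as examples for 999 in Figure 1's emergency tier.
5. Check that the training manual carries the same wording.

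The cost is a small wording amendment: one sentence in two places, an optional line in Figure 1, and a check of the manual. Under section 8.2 the sponsor decides whether the amendment is substantial; if it is, the REC responds within 35 days of receiving the notice. Emergency handling is already part of the planned training, so no session is added, and no extra staff or data are needed.
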